6.0 Data and Specimen Banking*

Not Applicable

7.0 Sharing of Results with Subjects*

Results will not be shared with subjects or others associated with the subject's medical care

8.0 Study Timelines*

All patients will participate in the following events shown in Table C.2. Follow up visits will be conducted during standard postoperative clinical visits or over the phone. We anticipate enrolling patients for 4 years with an additional 6 months needed to complete 6-month follow-up for all patients. We anticipate completing primary analyses at the end of 6 month follow-ups.

9.0 Inclusion and Exclusion Criteria*

Inclusion Criteria

- 1. Patients 18 years of age or older.
- 2. Extremity fracture.
- **3.** Prior definitive fracture management with external fixation, internal fixation, or joint fusion.
- **4.** Superficial, deep, or organ space SSI (as per CDC criteria) at the fracture site that requires operative management.
- 5. Will have all planned SSI care surgeries performed by a participating surgeon or delegate.
- 6. Provision of informed consent.

Exclusion Criteria

- 1. Fractures of the hand cannot be imaged.
- 2. Iodine allergy.
- **3.** Burns at the SSI site.
- 4. Incarceration.
- 5. Expected survival of less than 90 days.
- 6. Problems, in the judgment of study personnel, with maintaining follow-up with the patient.
- 7. Adults unable to consent or whom do not have a LAR
- 8. Individuals who are not yet adults (infants, children, teenagers)
- 9. Pregnant or breastfeeding women

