2.0 Background*

The focus of this study is to (1) Explore variability in distribution of 24h ICG in bone and soft tissue infection (2) Evaluate the change in 24h ICG distribution from pre to post debridement (3) Preliminarily determine whether 24h ICG has the possibility predict infection / treatment failure

Infection following trauma is one of the most prevalent and challenging complications faced by orthopedic surgeons in both military and civilian populations, occurring after up to 60% of open bone fractures¹⁻⁷. Several factors specific to this trauma place patients at high risk for infectious complications, including: traumatized tissues, open contaminated fracture, soft tissue coverage issues, catabolic state due to poly-trauma, prolonged hospitalization with exposure to nosocomial bacteria, and presence of metallic implants⁸. Infection requires one or more unplanned surgical procedures and leads to prolonged morbidity, loss of function, and potential loss of limb^{1, 9-11}. Failed treatment for bone infection results in recurrent infection, requiring repeat surgical procedures in approximately 30% of patients.¹²⁻¹⁵

We are currently enrolling patients into a study to evaluate the utility of first window ICG to identify areas of deficient perfusion. This is based upon the concept deficient perfusion prevents delivery of antibiotics and endogenous immune cells to traumatized tissues. In the setting of established infection, poorly perfused bone can be a nidus for biofilm formation creating resistance to antibiotics. However, in the context of this work it is becoming increasingly clear that acute (rather than chronic) infections display hyper vascularity with increased blood flow and neovascularization. Infection is known to display the enhanced permeability and retention effect with increased vascular permeability. Second window or 24h ICG represents an ideal method to identify these areas of increased vascular permeability. In some instances infected tissue can be hard to distinguish from healthy

v.26Oct2022

Page 4 of 21

tissue when ICG is given immediately before optical imaging Second window ICG will allow surgeons to better distinguish infected tissue from healthy tissue as the ICG will have a better opportunity to permeate the infected tissue while it will have been expelled from the health tissue.

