10.0 Vulnerable Populations*

In order to ensure that this study is not biased against patients with the most severe infections, who are most likely to benefit from this imaging device, patients who are cognitively impaired (most likely due to head trauma) will be eligible for this study.

A legally authorized representative (LAR) with reasonable knowledge of the potential participant will be approached to consent on the patient's behalf if the patient cannot adequately answer at least 2 questions about the study or it is determined that the patient's level of cognition is not likely to change before study medication (ICG) can be administered. These questions will be to assess the participant's understanding of the study and what it means to participate, their appreciation of the consequences of participation, and their ability to consider alternatives to participation.

The choice of LAR will follow standard procedures. The following with be approached in this order of priority:

- Legal guardian
- Proxy (health care agent) named in an advance directive or durable power of attorney for health care;
- Family member or other surrogate identified by the state law on health care decisions.

Guidance will be provided to assist the LAR in making the consent decision. They will advised to base the decision on the participant's expressed wishes, or, if these are not known, what they believe the participant would have desired under the circumstances of the injury, their beliefs and values. If the LAR does not know what the participant would have wanted, the LAR will advised to base the decision with the participant's best interest in mind. They will be asked to carefully consider how much leeway the participant would likely give the LAR in making the choice about participation in the study.

This is in compliance with Checklist HRP-417 (Cognitively Impaired Adults). **11.0 Local Number of Subjects**

This is a pilot study to investigate the feasibility of obtaining fluorescence imaging following injection of ICG 24 hours prior to surgery for infection. This study seeks to enroll 20 patients. Several studies by this investigator inject ICG during surgery, however none have investigated ICG injection prior to surgery. The data collected in this pilot study will inform future studies involving ICG injection and the optimal time of injection.

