12.0 Recruitment Methods

Participation in this research requires informed consent according to Institutional Review Board (IRB) guidelines and a signed IRB-approved Consent Form as the means of documenting this understanding.

Potential subjects will be identified either through the Orthopaedic outpatient clinic or by the patient's primary attending when the patient is currently an in-patient. Subjects who have undergone previous trauma surgeries and have developed an infection will be assessed for protocol inclusion criteria. This study requests a partial waiver of HIPAA for recruitment purposes. The partial waiver would allow for the surgeon to share with the research coordinator the patient name, sex, MRN number, age, underlying conditions as well as type and location of injury. There is an adequate plan to protect identifiers from improper use and disclosure as

information will only be used by study team members to determine whether a patient may be eligible. Information will only be communicated and stored using D-HH approved secure platforms. Information is only being used to determine if a patient is eligible for the study, for recruitment purposes. Once approached, if a patient is not interested, information will be destroyed. Protected health information will not be re-used or disclosed for another purpose. It will only be used for recruitment. This research could not practically be done without a partial waiver of HIPAA. This information is needed for recruitment. Patients will sign a full HIPAA Authorization when consenting to the study.

Subjects will be invited to participate in this study by a member of the orthopaedic care team, which will occur either at the time of consultation with the surgeon about the candidate's standard-of-care procedures or at another time agreed to by the potential participant, the candidate's surgeon or their designee. No advertisements or other promotional material will be used. No finder fees or recruitment incentives will be offered. Women of child bearing potential are eligible for enrollment into this study because ICG administration is not considered to present any additional risk for these women. The study will exclude women who are pregnant or breast-feeding as indicated in the exclusion criteria. Women of child-bearing potential, if asked to participate, will be given a pregnancy test as part of their standard of care testing prior to surgery and before administration of ICG.

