14.0 Risks to Subjects*

The risks to subjects are minimal in relation to anticipated benefits and/or knowledge that might reasonably be expected from the results of this clinical trial.

Risk of ICG injection: ICG (Indocyanine Green) will be administered intravenously once, 24h preoperatively. ICG is FDA approved for human use in angiography for ophthalmology and cardiology applications and is given routinely to patients in these clinical settings. The risks are considered minimal and consist of nausea, vomiting, hives, increased heart rate in subjects with particular sensitivity to the dye. ICG does contain sodium iodide and patients with a history of allergy to iodides will be excluded. Anaphylactic or urticardial reactions are rare but have been reported in patients both with and without a history of allergy to iodides. Anaphylactic deaths have been reported following IGG administration during cardiac catheterization. Reported rates of mild, moderate and severe adverse reactions to ICG are 0.15%, 0.2% and 0.05%. Every effort will be made to minimize this risk as much as possible. It is the standard of care at this institution to obtain information related to allergies, sensitivities and past medical histories upon patient arrival. Patients will also be monitored throughout their hospitalization, as is the standard of care, by everyone involved in their medical care for evidence of new or previously unknown reactions or sensitivities. Additionally, at all times ICG fluorescence imaging assessments are taking place, research staff and both surgical and anesthesia staff will monitor patients closely for any adverse reaction to ICG. Qualified inpatient medical staff or CRU staff will monitor patients for at least 30

minutes after ICG fluorescence injection has been completed. In the event of an unexpected allergic reaction, Dartmouth-Hitchcock Medical Center and all affiliated groups within this institution have procedures in place for managing patients with unknown or unexpected allergic reactions. If such a reaction were to occur, all standard of care treatments will be provided including but not limited to treatment with appropriate agents such as epinephrine, antihistamines and corticosteroids. Risk of infection from IV injection is also extremely rare but can occur. Pregnant women are excluded from the study. A pregnancy test is administered to women of child-bearing age on request at no cost.

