The risks to subjects are minimal in relation to anticipated benefits and/or knowledge that might reasonably be expected from the results of this clinical trial. ICG is FDA approved for human use in angiography for ophthalmology and cardiology applications and is given routinely to patients in these clinical settings. The risks are considered minimal and consist of nausea, vomiting, hives, increased heart rate in subjects with particular sensitivity to the dye. ICG does contain sodium iodide and patients with a history of allergy to iodides will be excluded. The ICG will be administered thru IV which the patient will have regardless of if they participate in this trial or not. There will be no additional study specific IV's placed.

ICG, the Spy Elite® imaging system and the Zeiss Pentero 800 surgical microscope are FDA approved for use in human subjects. Currently we are enrolling patients into a study to evaluate the utility of first window ICG to identify areas of deficient perfusion. This study seeks to evaluate ICG utility as a second window in areas of deficient perfusion. This study is to be conducted according to US and international standards of Good Clinical Practice (FDA Title 21 part 312 and International Conference on Harmonization guidelines), applicable government regulations and Institutional research policies and procedures.

Page 18 of 21

Patients with impaired decision-making capacity will be included in this study. If the patient is unable to provide informed consent (e.g. due to their injury) at the time they are identified, informed consent may be obtained from their legally authorized representative (LAR). Allowing informed consent from a patient's LAR will reduce the risk of recruitment bias against the most severely infected patients.

For patient with impaired decision-making capacity, a LAR with knowledge of the potential participant will be approached to consent on the patient's behalf. If the patient cannot adequately answer at least two questions about the study or it is determined that the patient's level of cognition is not likely to change before study medication (ICG) can be administered, their LAR will be approached.. These questions will be to assess the participant's understanding of the study and what it means to participate, their appreciation of the consequences of participation, and their ability to consider alternatives to participation.

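### The only allergy exclusion is iodine allergy, so a patient with a known allergic reaction to ICG itself is eligible as written

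*Protocol*

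**What the plan says.** Protocol section 9.0 lists six inclusion and nine exclusion criteria. One exclusion concerns allergy, number 2: "Iodine allergy". Section 21.0 gives the same scope: "ICG does contain sodium iodide and patients with a history of allergy to iodides will be excluded". Section 14.0 carries an identical sentence, so the rule is consistent across the protocol.

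On the hazard, section 14.0 states: "Anaphylactic or urticardial reactions are rare but have been reported in patients both with and without a history of allergy to iodides". It adds: "Anaphylactic deaths have been reported following IGG administration during cardiac catheterization" (the abbreviation there is evidently meant to be ICG). It gives reaction rates of 0.15% (mild), 0.2% (moderate) and 0.05% (severe). It also notes that allergies, sensitivities and medical history are recorded on arrival as standard of care, and that patients are watched for at least 30 minutes after the injection, with treatment for reactions available.

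Three statements bear on earlier exposure to the dye. Section 12.0 describes the candidates: "Subjects who have undergone previous trauma surgeries and have developed an infection will be assessed for protocol inclusion criteria". Section 11.0 says: "Several studies by this investigator inject ICG during surgery, however none have investigated ICG injection prior to surgery". Section 2.0 says: "We are currently enrolling patients into a study to evaluate the utility of first window ICG to identify areas of deficient perfusion".

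Dosing is described as single in sections 5.0 and 14.0, and section 15.0 states that participants gain no direct benefit.

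**The concern.** Iodine allergy stands in for allergy to a dye that contains sodium iodide. By the protocol's own account it is an incomplete stand-in, because reactions have also been seen in people with no iodide allergy. The most direct warning sign, a previous allergic reaction to ICG, appears nowhere in the eligibility criteria. Read literally, someone who has had anaphylaxis after ICG and carries no iodine-allergy label can be enrolled and dosed.

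At stake is a foreseeable and possibly severe reaction in a participant who stands to gain nothing directly from the dose. Eligibility is settled in the protocol, so this is not a detail that a statistical analysis plan would supply.

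**Working it through.** **Reading the rules together**

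- Section 9.0, exclusions: one of nine concerns allergy (iodine). None names ICG.
- Section 9.0, inclusions: none of the six concerns allergy.
- Section 13.0, withdrawal: the triggers are incomplete imaging, withdrawn consent, a clinical event that prevents imaging, and pregnancy before injection. An earlier reaction to ICG is not among them.
- Sections 14.0 and 21.0: both refer to iodide allergy only. Section 14.0 mentions subjects who are sensitive to the dye, but as a risk and not as a reason for exclusion.

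A patient who has reacted to ICG and is also labelled iodine-allergic is caught by exclusion 2. One without that label is not.

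**How many patients could this affect?**

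The protocol gives no figure for this, so there is none to reproduce. The inputs are:

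- N = 20 (sections 1.0 and 11.0).
- Reaction rate r per dose (section 14.0): severe only, 0.05%; any reaction, 0.15% + 0.2% + 0.05% = 0.40%. The protocol does not separate allergic from other reactions, so both are used as a range.
- p, the share of patients with earlier ICG exposure: not given; assumed 10%, 50% or 100%.
- d, earlier doses per exposed patient: not given; assumed 1, with 2 as a check, and doses treated as independent.

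Formulas:

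- q = p × (1 − (1 − r)^d), the chance that a given patient is a previous reactor
- Expected number = 20 × q
- P(at least one) = 1 − (1 − q)^20

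| p | d | Expected, severe only | Expected, any reaction | P(at least one), severe only | P(at least one), any reaction |
|---|---|---|---|---|---|
| 10% | 1 | 0.001 | 0.008 | 0.10% | 0.80% |
| 50% | 1 | 0.005 | 0.04 | 0.50% | 3.92% |
| 100% | 1 | 0.01 | 0.08 | 1.00% | 7.70% |
| 100% | 2 | 0.020 | 0.160 | 1.98% | 14.81% |

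Example: p = 100%, d = 1, any reaction gives 1 − 0.996^20 = 7.70%; with d = 2 it is 1 − 0.996^40 = 14.81%.

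The any-reaction columns run high for two reasons. They count mild reactions that need not be allergic, such as nausea, and they ignore reactors whom exclusion 2 already removes. All columns count previous reactors among the 20, not previous reactors who would actually be dosed, which would be fewer. Nor is the table an upper bound, because more earlier doses per patient would raise the figures.

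**The case against.** The strongest reply is that nothing here is wrong or contradictory. The rule is the same wherever it appears, and the risk section promises nothing wider. The quoted hazard mostly describes unpredictable first reactions, which the proposed wording would not prevent, and the protocol does not say that the reported deaths followed a known earlier reaction. For harm to occur, a documented dye allergy would have to pass the surgeon, the staff giving the dose, and the patient or representative, although allergies and sensitivities are recorded on arrival. Earlier exposure is inferred: section 12.0 speaks of previous trauma surgery, not previous ICG, and no passage says that patients from the investigator's other ICG studies enter this one. If they did, the same research group would be well placed to know of a reaction.

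Much of this stands. No contradiction is claimed, the overlap between studies is unknown, and the probabilities at 100% exposure deserve little weight. The dose is stated as single, so no argument rests on repeat dosing.

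What does not follow is that the rule can stay as it is. The history taken on arrival covers sensitivities in general, but no passage makes an ICG reaction found there a reason not to enrol or dose. Observation and treatment manage a reaction; they do not prevent one that could have been foreseen. Section 10.0 also deliberately includes cognitively impaired adults, who may be unable to report an earlier reaction themselves.

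**Conclusion.** The concern holds, at minor severity. Exclusion 2 is too narrow for the agent being given: known hypersensitivity to ICG without iodine allergy does not bar a patient from a dose of no direct benefit.

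The likely number affected is well below one patient in 20. The expected count is 0.001 to 0.008 if 10% had one earlier dose and 0.01 to 0.08 if all had. These figures rest on assumed exposure and on reaction rates that mix allergic with other reactions. The case for change rests on the possible severity of a reaction and the ease of the correction, not on frequency. Sample size, endpoint and analysis are not affected.

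**What to change.** Reword exclusion 2 in section 9.0 to: *Allergy to iodine or iodides, or known hypersensitivity (allergic or anaphylactic reaction) to ICG.* This wording leaves patients with isolated earlier nausea eligible. Bring the corresponding exclusion sentences in sections 14.0 and 21.0 into line. If ICG is ever given again for a repeat debridement, apply the same criterion before that dose.

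The cost is one eligibility line and two matching sentences, and the rare loss of an otherwise eligible patient.

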5.0 Procedures Involved*

Eligible patients regardless of ethnicity or health status, will be identified and recruited subject to inclusion and exclusion criteria above. Patients who meet eligibility criteria will be asked to participate in the trial. If they agree, written informed consent will be obtained from the patient or their healthcare proxy. To obtain informed consent, study personnel (surgeon or research coordinator) will adhere to the following procedures: (1) present study information in a manner that is understandable to the patient; (2) discuss the study with the patient and answer any questions; (3) allow the patient an opportunity to discuss participation with their family; (4) confirm that the patient understands the risks and benefits of participating in the study and that their participation is voluntary; (5) complete the consent process and obtain signatures from the patient and research team. The process of obtaining and documenting informed consent forms will be completed in accordance with local Good Clinical Practice (GCP) recommendations.

If the research team member obtaining consent is at all unsure about the patient's ability to consent, s/he will consult with the study PI.

This study seeks to include individuals with lacking or limited decision making capacity. A legally authorized representative (LAR) with reasonable knowledge of the potential participant will be approached to consent on the patient's behalf if the patient cannot adequately answer at least 2 questions about the study, or it is determined that the patient's level of cognition is not likely to change before study medication (ICG) can be administered. These questions will be to assess the participant's understanding of the study and

v.26Oct2022

Page 6 of 21

what it means to participate, their appreciation of the consequences of participation, and their ability to consider alternatives to participation.

The choice of LAR will follow standard procedures. The following with be approached in this order of priority:

- Legal guardian
- Proxy (health care agent) named in an advance directive or durable power of attorney for health care;
- Family member or other surrogate identified by the state law on health care decisions.

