18.0 Provisions to Protect the Privacy Interests of Subjects

Information about study subjects will be kept confidential and managed according to the requirements of the Health Insurance Portability and Accountability Act of 1996 (HIPAA). Risk of breach of confidentiality of the medical records and status of participants will be minimized. Databases which are used to store subject-sensitive information are password-protected and encrypted during file/data transfers from viewing terminals. Access will be limited to research team members who have undergone CPHS training at Dartmouth. Whenever possible and practical standard-of-care clinical data used in the research will be de-identified when under analysis. All data will be communicated in a HIPAA-compliant manner using a HIPAA-compliant database for clinical data (REDCap) and a HIPAA-compliant storage drive for imaging data. Clinical and imaging data will be uploaded to the appropriate HIPAA-compliant site by the local research team at each institution and all data will be analyzed at either Dartmouth Hitchcock Medical Center or Dartmouth College/Thayer School of Engineering. De-identified patient information using a Study ID number will be utilized when possible.

This study is to be conducted according to US and international standards of Good Clinical Practice (FDA Title 21 part 312 and International Conference on Harmonization guidelines), applicable government regulations and Institutional research policies and procedures.

All subjects for this study will be provided a consent form describing this study and providing sufficient information for subjects to make an informed decision about their

v.26Oct2022

Page 16 of 21

participation in this study. See Attachment for a copy of the Subject Informed Consent Form. This consent form will be submitted with the protocol for review and approval by the IRB. The formal consent of a subject, using the IRB-approved consent form, will be obtained before that subject undergoes any study procedure. The consent form will be signed by the subject or legally acceptable surrogate, and the investigator-designated research professional obtaining the consent.

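### Exclusion 7, as worded, bars adults who lack capacity even when a LAR can consent, although sections 5, 10 and 21 say they are to be enrolled

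*Protocol*

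**What the plan says.** Section 9.0 lists, as exclusion 7, "Adults unable to consent or whom do not have a LAR". Inclusion 6 in the same section reads only "Provision of informed consent" and does not say who may give it.

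Section 5.0 ties recruitment to the list: eligible patients "will be identified and recruited subject to inclusion and exclusion criteria above". The only such list is the one in section 9.0.

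The sections on capacity and consent take a single line:

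- Section 5.0: "This study seeks to include individuals with lacking or limited decision making capacity". It accepts consent from a healthcare proxy and sets out when and in what order a LAR is approached.
- Section 10.0: "patients who are cognitively impaired (most likely due to head trauma) will be eligible for this study". The stated reason is to avoid bias against the most severe infections.
- Section 18.0: "The consent form will be signed by the subject or legally acceptable surrogate".
- Section 21.0: "Patients with impaired decision-making capacity will be included in this study". It adds that "Allowing informed consent from a patient's LAR will reduce the risk of recruitment bias against the most severely infected patients", that leaving these patients out would harm generalizability, and that assent will not be sought from those who cannot consent for themselves.

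**The concern.** An exclusion list is applied item by item at screening, and meeting any one item disqualifies the patient. Exclusion 7 contains two conditions joined by *or*, so either is sufficient. A patient who cannot consent is therefore out, even with a LAR ready to sign. That is the group which sections 5.0, 10.0 and 21.0 set out to keep.

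Screening staff cannot satisfy both texts. If they apply the list as written, the study takes on the recruitment bias against severe infection that the protocol says it wants to avoid. If they follow the consent sections, every enrolment through a LAR goes against a written exclusion and is open to challenge under the regulatory-compliance monitoring in section 17.0. The people concerned are the vulnerable population of section 10.0, for whom the eligibility wording should leave no doubt.

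**Working it through.** The protocol gives no figure to reproduce here, so the check is logical. Classify a patient on two yes/no attributes, capacity to consent and availability of a LAR, which gives 2 × 2 = 4 combinations. Then apply each rule.

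**Rule A, exclusion 7 read literally (section 9.0):** exclude if the patient is unable to consent *or* has no LAR.

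**Rule B, the consent sections (5.0, 10.0, 18.0, 21.0):** the form must be signed by the subject or a surrogate. A patient is therefore ruled out only when neither can sign, that is, when the patient is unable to consent *and* has no LAR.

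| Capacity | LAR available | Rule A | Rule B | Agree? |
|---|---|---|---|---|
| Yes | Yes | not excluded | not excluded | yes |
| Yes | No | excluded | not excluded | **no** |
| No | Yes | excluded | not excluded | **no** |
| No | No | excluded | excluded | yes |

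Rule A excludes 3 combinations and Rule B excludes 1. The combination excluded by Rule B is also excluded by Rule A, so the rules disagree on 3 − 1 = 2 of the 4. Replacing *or* with *and* in Rule A makes it identical to Rule B, and the disagreement falls to 0.

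Two further checks:

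1. *Could inability to consent in exclusion 7 already mean inability both in person and through a LAR?* The protocol's own usage is against this. Section 21.0 uses nearly the same words for a patient whose LAR may then consent, and again for subjects already in the study from whom assent will not be asked. On that reading, the LAR clause of exclusion 7 would also be largely redundant.
2. *Does anything else settle it?* Inclusion 6 does not, because it is silent on who consents. No section refers to exclusion 7 or confines it to patients without a LAR.

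**The case against.** The best reply is that the intent is unmistakable. Exclusion 7 would hardly mention a LAR if everyone unable to consent were excluded anyway. Three sections describe the LAR route in detail: the trigger for approaching a LAR, the order of priority, and guidance on how the LAR should decide. Staff who read the whole protocol would probably understand the criterion as intended, and nothing in the document shows that they would apply it literally. The bias is therefore conditional.

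The reply also notes that the second disagreement, a capable adult with no LAR, has little practical weight. The protocol never asks whether a capable patient has a LAR, and section 18.0 lets the subject sign. Two of four counts logical combinations, not patients. Inclusion 6 is already compatible with LAR consent, so editing it is a matter of preference.

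Most of this is fair on weight. The *or* is very likely a slip, the capable-without-LAR combination is secondary, and the inclusion 6 edit is optional. None of it removes the contradiction. Exclusion 7 is an operative criterion, section 5.0 makes recruitment subject to it, and clear intent elsewhere does not change what the criterion says.

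**Conclusion.** The concern holds. As written, exclusion 7 contradicts sections 5.0, 10.0 and 21.0 for adults who lack capacity but have a LAR. It also literally excludes capable adults without a LAR, which the consent sections do not support; this shows that the wording is faulty but is not the main harm.

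The size can be stated only as a disagreement on two of four capacity-by-LAR combinations, one of them consequential. How many patients fall there cannot be derived, because section 21.0 says that some will be cognitively impaired without giving a figure. The target of 20 patients does not change. The recruitment-bias consequence assumes that screening staff apply the list literally; if they do not, the consequence is enrolment against a written exclusion. This is a drafting inconsistency in an eligibility rule, not a fault in the underlying decision to enrol through a LAR, and it should be corrected.

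**What to change.** Reword exclusion 7 to: *Adults who are unable to consent and do not have a LAR available to consent for them.* Optionally, for consistency with sections 5.0, 18.0 and 21.0, reword inclusion 6 to: *Informed consent given by the patient or by a LAR.*

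The cost is one or two single-line wording changes. Both carry out the intent that the protocol already states, and neither affects patient numbers, procedures or analysis.
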